Duration of Conditions: We have chosen 3-week duration for each Condition based on: 1) The results of co-Investigator, [name], showing maximal effect of TE2 on irritability symptoms within one week; 2) placebo-controlled studies showing TE2 reduces perimenopausal depression symptoms with maximal effects seen in one to three weeks;^{27,28} 3) withdrawal from TE2 increases depressive symptoms within one week in perimenopausal women with histories of perimenopausal depression;²⁹ and 4) clinical experience that maximal efficacy of TE2 for treating perimenopausal depression is evident within two weeks (personal communication, [name]). Thus, the beneficial mood effects of TE2 are rapid and detectable within 3 weeks. With the mean half-life of TE2 equal to 161 mins,³⁰ pharmacokinetic clearance is complete in 13 hours (five half-lives). We will employ a three-week washout window to minimize, if not eliminate, even lagged carryover effects³¹

3. Specific Aims

Alignment of the	Specific Aims with Measures	and Aim-Specific Statistical A	Analysis Plans
Specific Aim	Outcome Measures	Estimands	Statistical Estimators
(1) Determine baseline relationships:			
a) E1G variability and irritability symptoms	-Every-other-day baseline E1G measurements -weekly irritability score	-Standard deviation of 14 E1G measurements -average of 4 weekly irritability (IDAS) scores	Model-based estimates, all with 95% C.I., regression coefficients
b) E1G variability and neural oscillations	-E1G standard deviation -frontal theta (dB) during threat, parietal beta (dB) during frustration	-E1G standard deviation -average event-related theta (dB) during Dot Probe Paradigm/ average event-related beta (dB) during Affective Posner Paradigm	Model-based estimates, all with 95% C.I., regression coefficients
c) irritability symptoms and neural oscillations	-weekly irritability score -frontal theta, parietal beta	-average of 4 weekly irritability scores -frontal theta (dot probe), parietal beta (Affective Posner Paradigm)	Model-based estimates, all with 95% C.I., regression coefficients

(2) Determine effect of TE2 administration on:

a) neural oscillations -Event-related frontal

-Event-related frontal - Frontal theta during dot theta and parietal beta probe/Parietal beta during Affective Posner

Paradigm

Model-based estimates, all with

95% C.I.

b) irritability symptoms

-irritability symptoms

-IDAS irritability symptoms

Model based estimates

3.1. Aim 1

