4.2. Experimental Design

We have selected a within subjects, double-blind, cross-over design because of the greater statistical power over a between subjects RCT and to minimize bias.

Participants are randomized (1:1), without stratification, to order of TE2 versus transdermal placebo. Participants will receive either three weeks of transdermal E2 (0.1 mg/day) or three weeks of transdermal placebo as their first condition (Condition 1) and the other treatment (active E2 or placebo) as their second condition.

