5.1. Numbers of Participants

Number to be screened: N £ 135Number to be enrolled: N = 50

Up to 135 individuals will be screened. Based on our prior experience with perimenopausal women and intervention studies involving transdermal E2, we estimate that 40% will fail the medical screening for TE2 eligibility, and an additional 20% will not be interested in participating.

It will be necessary to enroll 50 perimenopausal women because our prior experience also suggests that 30% (n=15) will not meet eligibility for TE2 upon further screening, yielding about 35 eligible for the randomized, cross-over study. We conservatively account for 15% (n =5) withdrawal following randomization, yielding 30 women who complete the protocol

Since this is a cross-over study design, all enrolled women will receive both the active TE2 condition and the placebo TE2 condition.

Recruitment: Participants will be recruited through the Menopause Clinics at the UNC Hospitals, and through the UNC Center for Women's Mood Disorders. Additionally, participants will be respondents to advertisements in local newspapers, social media, and mass email listservs seeking volunteers for research. To increase minority applicants, physicians who are African American or of other minority ethnic groups will be included as referral resources, and certain ads will particularly request minority volunteers.

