- Daily assessment of irritability symptoms using the irritability subscale of the IDAS questionnaire participants will be prompted to complete this questionnaire at home using the HIPAA compliant
 Redcap software
- 4. At the end of week 3 of Condition 1, participants visit the lab in person at the end of baseline week 4 (+/- 2 days from day 21 of the Condition 1) and undergo EEG testing with Dot Probe and the Affective Posner Paradigm tasks

Visits 8-10 (weeks 1 - 3 of washout phase)

- 1. Side effects will be assessed via MyCap survey at the end of each week of the washout phase
- 2. Weekly assessment of mood using the CES-D questionnaire participants will be prompted to complete this questionnaire at home using the HIPAA compliant Redcap software
- 3. Daily assessment of irritability symptoms using the irritability subscale of the IDAS questionnaire participants will be prompted to complete this questionnaire at home using the HIPAA compliant Redcap software

Visits 11 - 13 (weeks 1 - 3 of Condition 2)

- 1. Side effects will be assessed by phone at the end of weeks 1-2 or in person at the end of week 3 during the home visit to collect urine strips.
- 2. Weekly assessment of mood using the CES-D questionnaire participants will be prompted to complete this questionnaire at home using the HIPAA compliant Redcap software
- 3. Daily assessment of irritability symptoms using the irritability subscale of the IDAS questionnaire participants will be prompted to complete this questionnaire at home using the HIPAA compliant Redcap software

4. At the end of week 3 of Condition 2, participants visit the lab in at the end of baseline week 4 (+/- 2 days from day 21 of the Condition 2) and undergo EEG testing with Dot Probe and the Affective Posner Paradigm tasks

Visit 14 (Progesterone Follow-up Phase)

1. Research staff will follow participants for up to 28 days or until bleeding ceases to document onset, duration and magnitude (degree of flow) of the progesterone-induced menstrual bleed

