7.5. Final Visit

Visit 14 (Prometrium phase)

At the end of the lab session for Condition 2, participants will be given their 10 day Prometrium (P4) supply with instructions for storage and schedule for administration (once per day, prior to bed). Research staff will follow participants until menstrual bleeding ceases with weekly phone calls to assess onset, duration and magnitude of the menstrual bleed (degree of flow from light to profuse). It is anticipated that menstrual bleeding with onset and cease within a 28 day window though we will continue to follow until it ceases.

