In sum, the Endocrine Society concludes that "Data from the various Women's Health Initiative studies, which involved women of average age 63, cannot be appropriately applied to calculate risks and benefits of menopausal hormone therapy in women starting shortly after menopause." ⁵⁰In fact, there is substantial evidence for the safety of E2, particularly if administered to women within 10 years of their final menstrual period and if administered as the transdermal form (e.g., lower risk of VTE). ^{50,54,55} Given our plans to administer transdermal E2 to women: 1) for only 3 weeks, 2) no older than 55 years of age, 3) who are still menstruating, albeit with variable cycle lengths, and 4) who are at no greater than average risk for CVD, breast cancer or VTE, the risk of serious adverse events is exceedingly low.

Psychological Risks: The structured interviews to assess current and lifetime psychiatric illness and suicide ideation and behavior and the Life Events survey may be associated with some psychological distress. Some items in the questionnaires may provoke some negative emotion in some individuals. There is also the risk a woman will experience the onset of a clinically significant affective episode, worsening of affective symptoms over the course of the 13-week protocol that would go undetected or untreated. There is the risk for emergent suicide ideation with intent or suicide attempts. However, importantly, there is no evidence that asking about suicidality increases suicidality—it actually tends to reduce it.⁵6However, because we are excluding women with past suicide attempts (the strongest predictor of future attempts) and excluding those at enrollment with any current suicide ideation with intent, combined with the requirement that suicide ideation (without intent) at enrollment be of low frequency and duration, the chance that suicide intent or behavior will emerge over the course of the 13 week study is remote. One third of Americans endorse suicide ideation at some point in their lives, ⁵⁷ yet less than 0.01% die by suicide each year. Because women in the MT are at increased risk for both ideation and attempts, ⁵⁸ we will include women with current suicide ideation if it is of mild severity (no intent) and limited frequency and duration (≤ once/week; < 1 hour/episode) as it does not predict imminent risk for a suicide attempt (in the absence of a history of multiple attempts).

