12.3. Assessment of Safety

- Side effects and AEs will be assessed at enrollment (in order to obtain a baseline levels of symptoms that
 may represent AEs in response to TE2) and again at baseline week 4 and weekly throughout the
 remainder of the study
- Vitals (blood pressure and weight) will be assessed at enrollment.
- Suicidality will be assessed during the enrollment with the MINI and weekly throughout the protocol using the suicide questions of the CES-D.
- Mood symptoms are assessed at enrollment with the IDAS and weekly with the CES-D throughout the protocol.
- Bleeding patterns are assessed at enrollment and again at weekly throughout the remainder of the study. At
 enrollment, if a participant reports experiencing prolonged menstrual periods (> 7 days) or profuse bleeding
 ('flooding' or bleeding through protection), [name] will perform an ultrasound of the endometrium to

determine if there is evidence of endometrial hyperplasia. In the event this is determined, the participant will be withdrawn from the study and referred for gynecological care.

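### The visit schedule lists no CES-D after Visit 13, although 4.3 and 12.3 promise it weekly for the whole study and about half the women have just stopped TE2

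*Combined protocol and SAP*

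**What the plan says.** **Text that runs the CES-D for the whole study.** Section 4.3 has the CES-D given weekly for the duration of the study. Section 12.3 states: "Suicidality will be assessed during the enrollment with the MINI and weekly throughout the protocol using the suicide questions of the CES-D". It says the same of mood symptoms. Section 7.6, on phone contacts, uses the same whole-study phrase and defines it as Visits 1 to 14. Section 12.5 has adverse events assessed weekly and expressly includes the progesterone follow-up month.

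**Text that lists nothing of the kind after Visit 13.** Section 7.4 gives, for washout and Condition 2, "Weekly assessment of mood using the CES-D questionnaire participants will be prompted to complete this questionnaire at home". For Visit 14 its only item is "Research staff will follow participants for up to 28 days or until bleeding ceases to document onset, duration and magnitude". Section 7.5 describes the contacts in that phase as "weekly phone calls to assess onset, duration and magnitude of the menstrual bleed". In the Table of Events (7.1) the IDAS and daily irritability rows end at Visit 13, and the CES-D has no row. The only Visit 14 marks are side effects and progesterone. Table 1 (4.3) ends daily irritability and AE/SAE documentation at Visit 13.

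**Study length.** Section 12.2 describes the psychological risk as "worsening of affective symptoms over the course of the 13-week protocol that would go undetected or untreated". The synopsis gives participation as sixteen weeks.

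**Why the period after TE2 matters.** Sections 2.2 and 4 cite evidence that "withdrawal from TE2 increases depressive symptoms within one week in perimenopausal women with histories of perimenopausal depression". Section 5.2.2 does not exclude women with that history.

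**What depends on the CES-D.** Section 7.8 keys its distress review to a CES-D total of 16 or more and its suicidality review to CES-D items 14 and 15.

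**The concern.** Every woman stops TE2 once, and randomization decides when. Those given it first stop at the start of washout, where the visit list has a weekly CES-D. Those given it second stop at the end of Condition 2 and go straight into the progesterone phase, where the visit list has none. Staff working from 7.4, 7.5 and the Table of Events would therefore not administer what 12.3 tells the IRB and the medical monitor to expect. In those weeks no scheduled instrument would supply the scores that the 7.8 reviews use.

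The documents themselves name the hazard and its timing. Section 12.2 adds that women in the transition are at increased risk of suicidal ideation and attempts, and that women with mild current ideation may enrol. At stake is the consistency of a safety procedure. Any descriptive account of mood events after stopping TE2 would also rest on different observation in the two sequences.

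**Working it through.** **Timeline.** Baseline 4 + Condition 1 3 + washout 3 + Condition 2 3 = 13 weeks. This reproduces the 13-week figure in 12.2, which therefore stops at Visit 13. Section 4 adds 3-4 weeks of follow-up: 13 + 3 = 16 and 13 + 4 = 17. The synopsis figure of sixteen weeks thus includes follow-up, and the 12.2 figure excludes it.

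**Women affected.** Section 4.2: "Participants are randomized (1:1), without stratification, to order of TE2 versus transdermal placebo". Section 5.1: "yielding about 35 eligible for the randomized, cross-over study". Half of 35 is 17.5, so 17-18 women receive TE2 second. Half of the 30 expected completers is 15.

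**Weekly mood scores scheduled after TE2 stops:**

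| Sequence | TE2 ends | Next phase | Weekly CES-Ds, visit lists in 7.4/7.5 | Weekly CES-Ds, if 12.3 covers follow-up |
|---|---|---|---|---|
| TE2 first | week 7 | washout, weeks 8-10 | 3 | 3 |
| TE2 second | week 13 | progesterone follow-up, weeks 14 to 16-17 | 0 | 3-4 |

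Daily irritability follows the visit-list pattern: it is collected through washout and not after Visit 13.

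**The sources side by side for the weeks after Visit 13:**

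| Source | CES-D and suicide items | Side effects / AEs |
|---|---|---|
| 4.3 text, 12.3 | weekly, whole study | weekly (12.3) |
| 7.6 | none stated; defines the whole-study phrase as Visits 1-14 | none stated beyond bleeding |
| 12.5 | none stated | weekly, follow-up month included |
| 7.4, 7.5 | not listed | bleeding only |
| Table of Events | no row at any visit | marked at Visit 14 |
| Table 1 | no row | ends at Visit 13 |

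There are two separate conflicts. One concerns the CES-D (4.3 text and 12.3 against the Visit 14 text in 7.4 and 7.5). The other concerns AE documentation (12.5 and the Table of Events against Table 1). The two study lengths leave it unclear whether references to the whole protocol include follow-up.

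**Does another instrument fill the gap?** The side-effects checklist continues and includes mood questions (7.3). Section 12.4 counts psychological deterioration and suicide intent or behavior as adverse events. No passage says that the checklist yields a CES-D total or items 14 and 15. The reporting text after the 12.5 table relies on IDAS cut-points and the IDAS suicide subscale, and the Table of Events stops the IDAS at Visit 13 as well.

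**The case against.** The strongest reply is that the intent is already clear. Sections 4.3 and 12.3 promise weekly collection, and 7.6 defines the whole-study phrase as reaching Visit 14. Section 7.8 asks women who leave the interventions to go on with surveys over the time of their 14 visits. Silence in 7.4 is also weak evidence. Its Visit 14 list omits side effects too, which the Table of Events requires there. Its Visits 5-7 list names the IDAS as the weekly mood measure where the other phases name the CES-D. The Table of Events omits the CES-D at every visit, so its Visit 14 column does not show when the CES-D stops. This shows that the sponsor probably did not decide to stop. It does not remove the conflict, because the lists and tables are what staff carry out.

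Four stronger readings are tempting, and the documents do not support them:

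- *Mood and suicidality monitoring ends at Visit 13.* Weekly AE interviews with mood and suicidality content continue in follow-up (7.1, 7.3, 12.4, 12.5).
- *A depressive episode or suicidality after Visit 13 could not reach the 7.8 actions.* The 7.8 criteria are worded as events, which an AE interview can reveal, and Appendix 5 gives actions for suicide intent, plan and behavior without tying them to the CES-D.
- *All 17-18 women face the cited withdrawal effect.* It is cited only for women with past perimenopausal depression. That history is neither required nor excluded, and its frequency is not given.
- *The treatment comparison is biased.* No aim, estimand or model concerns mood after TE2 stops, and the Aim 2 comparison ends with Condition 2.

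**Conclusion.** The contradiction is real and bears on participant safety. On the visit lists as written, the TE2-first sequence has three weekly CES-Ds after TE2 and the TE2-second sequence (about 17-18 of 35 randomized, 15 of 30 completers) has none. If 12.3 is read to include follow-up, the second figure becomes 3-4 and the imbalance disappears. The documents do not settle which reading applies.

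Monitoring under the visit lists is reduced, not absent. What is missing is any scheduled source for the CES-D scores that 7.8 uses, in the weeks when the protocol's own citation places a mood risk for some women. The size rests on the planned numbers in 5.1 and an even split. The number of women with the relevant history lies somewhere between none and all of the 17-18, and the documents give no basis for narrowing that. This is an internal inconsistency to be resolved. It is no evidence of a flaw in the crossover design or the efficacy analysis.

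**What to change.** Reconcile the synopsis, the 4.3 text, Table 1, the Table of Events, the Visit 14 text in 7.4 and 7.5, 12.2, 12.3 and 12.5. All should state the same period for four things: the weekly CES-D, its suicide items, the 7.8 reviews that use them, and AE/SAE documentation. Give the CES-D a row in the Table of Events. Make the 13-week and sixteen-week figures agree, or say which phases each one counts. If the side-effects checklist is meant to serve in place of the CES-D after Visit 13, the documents should say so and say how it connects to 7.8. Which monitoring applies in follow-up is for the sponsor and the responsible clinicians to decide. No threshold or withdrawal rule needs to change to remove the contradiction.

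The cost is a short amendment. If the sponsor confirms the coverage 12.3 already states, add up to about 4 app surveys per woman: 4 × 30 = 120 to 4 × 35 = 140 in total. They would use the existing REDCap/MyCap set-up and the staff who already make weekly calls in that phase.

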7.5. Final Visit

Visit 14 (Prometrium phase)

At the end of the lab session for Condition 2, participants will be given their 10 day Prometrium (P4) supply with instructions for storage and schedule for administration (once per day, prior to bed). Research staff will follow participants until menstrual bleeding ceases with weekly phone calls to assess onset, duration and magnitude of the menstrual bleed (degree of flow from light to profuse). It is anticipated that menstrual bleeding with onset and cease within a 28 day window though we will continue to follow until it ceases.

7.6. Phone Contacts

Phone calls will be used to collect initial screening and eligibility data (prior to study Day 0). Throughout the study (Visits 1-14) phone calls will be used to remind participants of the timing for replacing their patches, to schedule home visit times to collect urine and assess AEs and vitals, to schedule lab visits, and to monitor menstrual bleeding following P4-administration.

7.7. Follow-Up Contact

As described above, we will follow the participant until menstrual bleeding ceases following the progesterone administration. We will document the onset, duration, and magnitude of menstrual bleeding. [name] (gynecologist collaborator) will be contacted to follow up with the participant should bleeding persist for longer than 14 days or should it be prolonged (defined as bleeding or spotting that lasts more than 14 days consecutively or profuse (defined as more than one tampon or pad per hour on any one day or more than 3 tampons or pads per day for more than 3 days).

7.8. Early Discontinuations

Data to be Collected

If a participant chooses to withdraw consent or discontinue with the study interventions no medical records data will be collected at any point, however the following procedures will employed:

- 1. We will ask participant the reason for their withdrawal and record that in in their file and in the study database
- We will attempt to meet with the participant for one last visit to collect used/unused patches to determine compliance up to that point, assess and document vitals, and collect any E1G stored or unused urine strips.
- 3. If the participant wishes to withdraw from the intervention conditions, we will ask if they remain willing to complete the self-report surveys, particularly the irritability symptom scale on a daily basis, throughout the remainder of time that would correspond to their 14 study visits as irritability symptomatology is the primary outcome variable.
- 4. If the participant withdraws during or after at least one of the Conditions (TE2 or Placebo), the study gynecologist, [name] will be unblinded and determine if the participant needs the progesterone intervention for uterine protection. If that is determined to be the case, in order to

maintain the blind for research staff and the PI, [name] will be the one to follow the participant and document menses onset, duration, and magnitude associated with the Prometrium.

Criteria for Intervention Discontinuation

An individual will be withdrawn from the study by the investigators under any of the following conditions:

- 1. Inability to tolerate the adhesive in the patches
- 2. If there is indication of psychological distress that impairs function and would warrant treatment. We will monitor the CES-D in real time, on a weekly basis. If the clinical cut point with diagnostic specificity for Major Depressive Disorder (score ≥ 16), [name] will follow-up to assess psychological distress and determine if the participant is able to continue in the study. [name] will determine the next course of action (i.e., participant may continue or will be withdrawn and referred to the UNC Center for Women's Mood Disorders)
- 3. Emergent suicide ideation with intent or suicide behaviors. We will monitor the suicide questions (#s 14, 15) on the CES-D in real time, on a weekly basis. #14: I thought about my own death; #15: I thought about hurting myself. Question #14: I wished I were dead; #15: I wanted to hurt myself. Although endorsing these questions in and of themselves does not indicate imminent risk for suicide behaviors, a response of 4 on a 1 5 scale on any of these items (0 = not at all or less than 1 day; 2 = 1-2 days; 3 = 3-4 days; 4 = 5-7 days; 5 = nearly every day for the past week) will trigger a review by [name], who holds a master's in counseling psychology, or [name]. They will use their clinical judgement based on the number of other suicide risk items endorsed and the magnitude of thoughts or experiences (scores of 4 5) to determine if a follow-up assessment is warranted to ascertain more detail about these thoughts, including suicide intent and access to means. Someone with suicide ideation with intent or who has engaged in suicide behaviors will be withdrawn and referred for treatment.
- 4. Start of an exclusionary medication. At each study visit we will ask if the participant has started or stopped any medication or hormonal agent. The research staff will compare with the list of allowable and exclusionary medications.
- 5. Failure or inability to comply with study procedures as determined by the staff and ultimately by [name].
- Development of an exclusionary condition such as migraine with aura, deep vein thrombosis, diabetes.

